**Table 2: Analysis Windows**

Analysis Visit	Target Study Day	Protocol Visit Window (days)	Analysis Window (days)
Screening	-14	± 5	NA
Baseline	1	0	NA
Day 7	8	± 2	2 to 16
Month 1	31	± 6	17 to 46
Month 2	61	± 6	47 to 76
Month 3	91	± 6	77 to 106
Month 4	121	± 6	107 to 136
Month 5	151	± 6	137 to 166
Month 6	181	± 6	167 to 196
Month 7	211	± 6	197 to 226
Month 8	241	± 6	227 to 256
Month 9	271	± 6	257 to 286

## Statistical Analysis Plan

---

Analysis Visit	Target Study Day	Protocol Visit Window (days)	Analysis Window (days)
Month 10	301	± 6	287 to 316
Month 11	331	± 6	317 to 346
Month 12	361	± 6	347 to 376
Month 15	451	± 14	412 to 481
Month 18	541	± 14	511 to 571
EOS	541	± 14	Final Assessment

EOS = End of Study

### 6.4. SUBGROUPS

The following subgroups will be considered:

- Country: Australia, New Zealand and United States
- Reticular pseudodrusen at baseline: present, absent
- Age group: split into 3 similar sized groups (<75 years, 75-<85 years, ≥85 years)
- LL-VA deficit at baseline: < overall median value, ≥ overall median value
- Fellow-eye CNV at baseline: yes, no
- GA presence at baseline: unilateral, bilateral
- GA lesion size in the study eye: < 10 mm^2, ≥ 10 mm^2
- Sex: male, female

## 7. DEMOGRAPHIC, OTHER BASELINE CHARACTERISTICS AND MEDICATION

### 7.1. PATIENT DISPOSITION AND WITHDRAWALS

For the screened population the number of subjects screened, the number who failed screening and the reason for screen failure will be presented. For the ITT population the following will be presented by treatment group and overall:

- Number of subjects randomized
- Number of subjects completed treatment
- Number of subjects withdrawn from treatment and reason for withdrawal
- Number of subjects completed study
- Number of subjects withdrawn from study and reason for withdrawal
- Number of subjects in each analysis population and reason for exclusion from the PP population

The number of subjects randomized, completed treatment, withdrawn from treatment, completed study and withdrawn from study at each site will also be summarized.

## Statistical Analysis Plan

---

A summary of disposition by visit and by treatment group and overall will also be presented for the ITT and MITT populations. This disposition will be split by those receiving treatment (i.e. ongoing in study at the time of the visit) and those discontinued treatment prior to visit, and will include the following:

- Number of subjects ongoing in study at time of visit
  - Number of subjects attended visit
  - Number of subjects receiving injection
  - Number of subjects discontinued treatment prior to visit
  - Number of subjects missed visit
- Number of subjects discontinued study prior to visit

### **7.2. DEMOGRAPHIC CHARACTERISTICS**

Demography (gender, race, ethnicity, age [years], country) will be summarized for the ITT and MITT populations by treatment group and overall. Age will be summarized using summary statistics for continuous variables. Categorical age (<65 years, 65-<75 years, 75-<85 years and ≥85 years), gender, race, ethnicity and country will be summarized using summary statistics for categorical variables.

Age = (informed consent date - date of birth + 1)/365.25 truncated to complete years.

### **7.3. BASELINE CHARACTERISTICS**

Baseline characteristics (GA lesion size (FAF), BCVA, LL-BCVA, drusen size, IOP, LL-VA deficit, GA presence in the fellow eye, presence of reticular pseudodrusen, fellow eye CNV presence and study eye) will be summarized for the ITT and MITT populations by treatment group and overall. GA lesion size, BCVA, LL-BCVA, drusen size, IOP, LL-VA deficit and presence of reticular pseudodrusen will be summarized separately for the study eye and the fellow eye. GA lesion size (measured by FAF), BCVA, LL-BCVA and study eye IOP will be summarized using summary statistics for continuous variables. Drusen size (none, small, intermediate or large), LL-VA deficit (< overall median value, ≥ overall median value), GA presence in the fellow eye (yes, no), presence of reticular pseudodrusen, fellow eye CNV presence and study eye (OD, OS) will be summarized using summary statistics for categorical variables.

### **7.4. MEDICAL HISTORY AND CONCOMITANT DISEASES**

Medical history will be coded using the latest Medical Dictionary for Regulatory Activities (MedDRA) Version available. Summaries will be presented for the ITT and MITT populations by System Organ Class (SOC) and Preferred Term (PT) with counts and percentages by treatment group and overall. Each subject will be counted only once in each SOC or SOC/PT summary.

All ocular history, will be summarized for the ITT and MITT populations by System Organ Class (SOC)

## Statistical Analysis Plan

---

and Preferred Term (PT) with counts and percentages by treatment group and overall. The summaries will be produced separately for the study eye and the fellow eye. Any ocular condition associated with both eyes will be included in both summaries.

### **7.5. PRIOR AND CONCOMITANT MEDICATIONS**

Prior and concomitant medications will be coded using the latest WHO Drug Dictionary version available. Medication will be presented for the safety population by ATC level 2 (therapeutic main group) and ATC level 5 (standardized medication name) with counts and percentages by treatment group and overall. A subject who took more than one medication will be counted only once if these medications belong to the same extended ATC classification. In addition, prior and concomitant medications used in study eye will be summarized. Similar summaries will be provided for the medications used in the fellow eye.

Prior medications will be defined as those medications started prior to the administration of study drug on Day 1. Concomitant medications will be defined as those medications taken following the first administration of study drug on Day 1. Hence medications started before study dosing, but continuing after are considered as both prior and concomitant medications. The listing of medications will identify prior and concomitant medications.

If either the start or stop date of medication is missing, the worst or most conservative case will be considered when assigning medications to categories. So for a missing start date (where stop date is after date of first dose or missing) the date will be imputed as the date of first dose; for a missing stop date the date will be imputed as the last study date. If a partial date is recorded, the following convention will be used to assign the medication:

- If a partial date is missing a start day and the month/year is the same as first dose date then use first dose date, else '01' will be used for the day; if a start date is missing a month and the year is the same as first dose date then use first dose date, else January will be used for the start month.
- If a partial date is missing a stop day and month/year is same as last study date then use last study date, else last day of the given month will be used for the stop day; if a stop date is missing a month and the year is the same as last study date then use last study date, else December will be used for the stop month.

### **7.6. EXTENT OF EXPOSURE**

The number of injections, number of missed injections and duration of treatment will be summarized by treatment group for the ITT and MITT populations using frequency counts and percentages. The number of subjects receiving injections at each of the Months (1-12) will also be summarized by treatment group using frequency counts and percentages. As treatment is administered in the clinic there is no need to assess compliance.

## Statistical Analysis Plan

---

Duration of treatment (days) = date of last injection – date of first injection +1

The number of missed injections is defined as the scheduled injections missed up to discontinuation of study treatment.

Study drug administration will be listed by treatment group. In addition, a listing of total number of injections, duration of treatment, date and day of first and last dose and number of missed injections will be provided.

### **8. EFFICACY**

For the primary 12-month analyses, all efficacy data up to Month 12 will be included. For the final 18-month database lock, all by-visit summaries and analyses of change from baseline over time that are specified in this section, whenever applicable, will be repeated to include all data up to Month 18. The summary or analysis of data at Month 12 will be repeated for the data at Month 18.

#### **8.1. PRIMARY EFFICACY ENDPOINT AND ANALYSIS**

The primary endpoint is the change from baseline in square root area for GA lesion at Month 12 as measured by FAF. Baseline will be taken as the last available non-missing assessment prior to first study drug administration, this should be the screening assessment for the primary endpoint.

The change from baseline in square root area for GA lesion at Month 2, 6 and 12 will be analysed for the MITT population with a MMRM. The model will include the fixed effects of treatment (3 groups: AM, AEOM and Sham), baseline square root area for GA lesion, visit (2, 6 and 12 months), treatment by visit interaction, visit by baseline interaction and treatment by baseline interaction. An unstructured covariance structure will be used to model the within subject error. The Kenward-Rogers approximation will be used to estimate the denominator degrees of freedom. If the treatment by baseline interaction is not significant at the 10% level then this term will be removed from the model. If significant at the 10% level results will be presented both including and excluding this term and the nature of the interaction will be investigated before deciding on an approach for presenting results that include the treatment by baseline interaction.

All available data will be included in the analysis. The analysis model table will be presented. The treatment comparisons (AM vs Sham, AEOM vs Sham and AM vs AEOM) at Months 2, 6 and 12 will also be presented with the estimate, standard error and 95% CI. If the treatment effect is significant at the 10% level then the treatment means will be compared using the least significant difference (LSD) method and the p-value presented. In addition, the estimated mean (i.e. Least-Squares mean) change from baseline in square root area for GA lesion with  $\pm$  SE of mean change, will be plotted over time by treatment group.

The model assumptions will be checked by evaluating the model residuals. A Shapiro-Wilks test will

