11.2.3.1 Statistical Hypothesis

The null and alternative hypotheses for this study are:

$H_0: \mu_S = \mu_{AM} = \mu_{AEOM}$ vs $H_A: \mu_i = \mu_j$ for $i \in \{S, AM\}; j \in \{AM, AEOM\}$ and where μ indicates each groups respective 12 month change in square root lesion area .

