11.2.3.2 Analytic Methods

Since prior studies have demonstrated that square root area changes are independent of baseline size,^{1,2} we anticipate analysis with one factor Analysis of Variance (ANOVA) and no need for a baseline covariance correction or baseline size stratification. If the overall hypothesis of equality of group means (H_0) is rejected at the 0.1 alpha level, then group means will be compared with post-hoc Least Significant Difference (LSD) multiple comparisons. These multiple comparisons will also be conducted at the 0.1 alpha level.

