### **8.1.1. Sensitivity Analyses of the Primary Endpoint**

The robustness of the primary analysis will be evaluated by repeating the primary analysis with the per-protocol population.

In addition, the following sensitivity analyses will be conducted using the MITT population:

- A MMRM analysis including only data which is within a specific time period of the last injection. Month 6 data will be included if a subject was dosed on or after Month 4, and Month 12 will be included if a subject was dosed on or after Month 8. All Month 2 data will be included, as the criteria to be included in the MITT population requires a subject to have had at least one dose of study medication. The primary analysis will be repeated using this subset of data.
- An analysis using an LOCF method for handling missing data as specified in Section 6.2.1. All available Month 12 data will be included and missing data will be replaced using LOCF method. An analysis of Covariance (ANCOVA) model will be fitted for the Month 12 change from baseline in square root area for GA lesion, that includes baseline as a covariate and treatment (3 groups: AM, AEOM and Sham).
- Completer analysis i.e. observed data for those subjects who complete the treatment period (for subjects receiving monthly injections this will be 12 injections and for subjects receiving EOM injections this will be 6 injections) and have their Month 12 assessment. The analysis model will be the same as for the primary analysis.

For each approach, a summary over time will be presented. The analysis model table will be presented. The treatment comparisons (AM vs Sham, AEOM vs Sham and AM vs AEOM) will also be presented with the estimate, standard error and 95% CI. If the treatment effect is significant at

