## Statistical Analysis Plan

---

the 10% level then the treatment means will be compared using the least significant difference (LSD) method and the p-value presented.

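### SAP 8.1.3 treats LSD t-tests as a multiplicity adjustment without requiring a significant ANOVA; separately, SAP 8.1 does not name the visit of the test that releases its pairwise p-values

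*SAP*

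**What the plan says.** **Protocol.** Section 11.2.3.1 states a null of equal group means, where each mean "indicates each groups respective 12 month change in square root lesion area". Section 11.2.3.2 tests that null by one-factor ANOVA at 0.1. Only on rejection does it go on: "then group means will be compared with post-hoc Least Significant Difference (LSD) multiple comparisons", again at 0.1.

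**SAP 8.1.** The endpoint is fixed: "The primary endpoint is the change from baseline in square root area for GA lesion at Month 12 as measured by FAF". The analysis is one MMRM on the mITT population. Its terms include treatment, baseline, "visit (2, 6 and 12 months), treatment by visit interaction, visit by baseline interaction" and treatment by baseline (dropped if not significant at 10%). Three pairwise comparisons are shown at each of three visits, with estimate, standard error and 95% CI. P-values follow a condition: "If the treatment effect is significant at the 10% level then the treatment means will be compared" by LSD. No visit, contrast or degrees of freedom is attached to that condition.

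**SAP 8.1.1.** One shared sentence ("the 10% level then the treatment means will be compared using the least significant difference") covers all the sensitivity analyses. One of these has a single visit: "An analysis of Covariance (ANCOVA) model will be fitted for the Month 12 change from baseline".

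**SAP 8.1.3 and 4.1.** Growth over Months 6 to 12, 12 to 18 and 6 to 18 is compared by one-way ANOVA, on the square-root and untransformed scales. The pairwise comparisons use LSD t-tests, and the stated purpose is to adjust for multiplicity. Nothing makes them depend on the ANOVA result.

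**SAP 6.1** says that multiple comparisons will not be adjusted for. **SAP 2** gives the SAP precedence over the protocol on analysis. **SAP 13 item 3** discloses the move from ANOVA to MMRM, with missing data as the reason, and does not restate the release rule.

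**The concern.** The two parts carry different weight.

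**8.1.3 is wrong as written.** LSD tests each pair at the full 10% level. Any protection comes from the F test that must be passed first. Protocol 11.2.3.2 writes that condition down; 8.1.3 does not, yet claims the adjustment. A reader of the CSR addendum could take unadjusted p-values as adjusted.

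**8.1 is ambiguous.** In a model with a treatment-by-visit term, the treatment row of the model table is normally an average over Months 2, 6 and 12. That is not the protocol's hypothesis. If treatment by baseline is kept, the row also depends on how baseline is coded. Two programmers could therefore release or withhold the Month 12 p-values on different tests. The two tests need not agree if the treatment difference is not steady over time. SAP 8.1.3 itself reports that active-group growth in Months 6 to 12 differed from growth up to Month 6 (direction not given), so a linear course cannot be taken for granted.

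**Working it through.** **Step 1: reproduce the plan's power.** Inputs: means and 67 per group from Protocol 11.3.3; SD 0.20 (SAP 13 item 5 says this value was used); two-sided alpha 0.10. Power is noncentral F with 2 and 198 df and λ = n Σ(μᵢ − μ̄)² / σ².
- 0.23/0.23/0.33 (and 0.23/0.33/0.33): Σ = (2/3)(0.10)² = 0.006667; λ = 67 × 0.006667 / 0.04 = 11.17; power 91.4% (plan: 91%).
- 0.23/0.28/0.33: Σ = 0.005; λ = 8.375; power 82.6% (plan: 83%).

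**Step 2: LSD in 8.1.3.** Assumed: the three analysis groups of 8.1 (AM, AEOM, pooled sham), equal size, 198 df.
- Each pair is tested at |t| > t(0.95, 198) = 1.653. Some pair is significant when the studentized range exceeds 1.653 × √2 = 2.337.
- Unconditional: P(range of 3 groups, 198 df > 2.337) = 0.226.
- Conditional on F significant at 0.10: 0.100 (simulation, 1,000,000 trials). With exactly three groups, if two means are equal and the third differs, only one true null pair remains, so 10% holds there too.
- Three intervals on two scales make six such families. Even the conditional version controls error only within one of them.

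**Step 3: Month 12 test versus visit-averaged test in 8.1.** The documents give no visit covariance or time course, so two assumed sets are used, both with Month 12 SD 0.20.
- Set A: change = slope × t + eⱼ − e₀, with t = 2/12, 6/12, 1 and image-error SD s from 0 to 0.10 mm. Variance of the three-visit mean = (0.04 − 2s²)(5/9)² + (4/3)s². SD = 0.111 at s = 0 and 0.140 at s = 0.10.
- Set B: visit SDs 0.08/0.14/0.20, common correlation ρ. Variance = (0.066 + 2ρ × 0.0552)/9. SD = 0.105 at ρ = 0.3 and 0.131 at ρ = 0.8.

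In the 0.23/0.23/0.33 case, λ = 67 × (2/3) × (d/SD)², where d is the average of the three visit differences.

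| Course of effect (share of the Month 12 effect at Months 2, 6, 12) | d (mm) | Set | Power, averaged test | Power, Month 12 test |
|---|---|---|---|---|
| Linear (1/6, 1/2, 1) | 0.0556 | A | 91.4% to 76.2% | 91.4% |
| Linear | 0.0556 | B | 94% to 81% | 91.4% |
| Late (0, 0.25, 1) | 0.0417 | A | 72% to 54% | 91.4% |
| After Month 6 only (0, 0, 1) | 0.0333 | B | 59% to 43% | 91.4% |
| Front-loaded (0.33, 0.75, 1) | 0.0693 | A | 98.5% to 91% | 91.4% |

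Example: linear, set B, ρ = 0.3: d/SD = 0.0556/0.105 = 0.529; λ = 44.67 × 0.280 = 12.5; power 94%.

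Under the global null, the chance of a false Month 12 pair is about 10% with the Month 12 test and about 8% to 10% with the averaged one.

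**The case against.** **On 8.1, the text favours Month 12.** The endpoint sentence and the protocol null both fix that visit. The shared sentence in 8.1.1 can only mean Month 12 for the LOCF ANCOVA. SAP 8 refers to Month 12 as the analysis visit ("The summary or analysis of data at Month 12 will be repeated for the data at Month 18"), and Section 13 gives missing data, not a new hypothesis, as the reason for the MMRM. This stands. A reader might infer that the SAP has switched the primary test to a visit average; the documents do not say so.

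**The power figures rest on assumptions.** This also stands. Both sets use complete data without baseline terms. The zero-error end of set A makes the visits perfectly correlated, a case in which an unstructured covariance could not be fitted. A reader might infer that the averaged test can only lose power under a linear effect, or that the tests agree only with linear growth and negligible image error. Set B shows otherwise, with 94% against 91%. A familywise error near 14% at Month 12 needs an early effect that has vanished by then, and the documents describe no such course.

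**The wording reaches less far than it may seem.** SAP 8.1.2 has no release sentence. Its untransformed-area and completer analyses inherit the model only; the subgroups alone inherit the analysis approach.

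**On 8.1.3, naming an ANOVA before LSD suggests the protected sequence.** That is a fair reading of intent and the section is exploratory. But the condition is unwritten, and the claim of adjustment contradicts 6.1 on either reading.

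**Conclusion.** The 8.1.3 statement is wrong as written. Familywise error is 22.6% per interval and scale if LSD is unconditional and 10% if the F test is required. This rests only on three equal groups tested at 0.10.

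The 8.1 point is a real ambiguity of lesser weight. Month 12 is the likelier intent, but the literal treatment row tests something else. Its size cannot be fixed from the documents. Against 91% for the Month 12 test, the averaged test can be higher or lower for a linear effect (about 76% to 94%), is clearly lower for a late one (about 43% to 72%), and is about equal or higher for a front-loaded one (91% to 98.5%). A reader might infer inflated type I error for the primary analysis; under the global null neither test exceeds about 10%. Month 12 estimates, standard errors and 95% CIs are shown in every case, so only the formal test and its p-values are affected.

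**What to change.** 1. **SAP 8.1.3:** carry out LSD only if that interval's ANOVA F test has p < 0.10, and say that control holds within one interval and one scale. Otherwise remove the claim of adjustment and label the p-values unadjusted, in line with 6.1.
2. **Record first** which test released the p-values at the 12-month lock.
3. **SAP 8.1:** define the release test as the 2-df MMRM contrast AM = AEOM = Sham at Month 12, at 10% (at mean baseline if treatment by baseline is kept), and state that it releases the Month 12 LSD p-values.
4. **Use the matching endpoint visit** wherever the sentence recurs (8.1.1, 8.2.1, 8.2.3 to 8.2.5, 8.2.7), in the 8.1.2 subgroups, and at Month 18 in the 18-month repeats.
5. **Report it** as a clarification made after the 12-month results were seen. If the test actually run was a different one, report both.

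Cost: a few sentences and one contrast statement per model; no new data. Early differences would no longer help to open the comparisons, so a front-loaded effect could lose about 7 points (98.5% to 91.4% in the illustration). Rewording now cannot restore prespecification, which is why item 2 comes before the change to 8.1.

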## Statistical Analysis Plan

---

be performed on the residuals; a p-value  $> 0.1$  will be considered proof of normality. If a Shapiro-Wilks p-value is  $\leq 0.1$ , the residual plots will be evaluated for symmetry. If the evaluation of residuals indicates a problem with the model assumptions, another transformation of the data will be considered.

The change from baseline in square root area for GA lesion will be summarized by treatment group and visit for the MITT population using the observed data and replacing missing values with predicted values from the model. Summaries will present the descriptive statistics for baseline, absolute values and change from baseline data. The absolute values for missing data will be derived as the predicted change from baseline in square root area for GA lesion plus observed baseline value.

The observed values for the square root area for GA lesion will be summarized by treatment group and visit for the MITT population. Summaries will present the descriptive statistics for baseline, absolute values and change from baseline data. The observed mean change from baseline in square root area for GA lesion with  $\pm$  SE of mean change, will be plotted over time by treatment group.

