5.2 Study Endpoints

5.3 Primary Efficacy Endpoint

To demonstrate superiority of monthly and EOM APL-2 IVT injections compared to sham injections based upon the mean change in GA lesion size as measured by FAF.

- The primary endpoint is the change in square root GA lesion size from baseline to Month 12 as measured by FAF.

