11.3.1 Natural history growth rates

Based on two assessments of GA growth measured with Cirrus OCT,^{32,33} we assume that in the absence of treatment average square root area lesion growth is 0.33mm/year (mean of 0.28mm/year³³ and 0.37mm/year³²) and the standard deviation of annual square root area growth is 0.21mm/year.³²

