11.3.3 Treatment efficacy and power analysis

This study is designed to detect a 30% reduction in annual square root area increase. Calculations are provided for three scenarios (Proc Power onewayanova, SAS 9.3)

Square root area change (mm)			Sample size			Power to detect a difference
AM	AEOM	S	AM	AEOM	S	
0.23	0.23	0.33	67	67	67	91%
0.23	0.33	0.33	67	67	67	91%
0.23	0.28	0.33	67	67	67	83%

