### 3.4. TREATMENT ASSIGNMENT AND BLINDING

Each subject will be assigned a unique screening number upon entering screening. Subjects who complete the study screening assessments and meet all eligibility criteria will be scheduled to enter the study and be randomized. The randomization of subjects will be done via a web-based randomization system (IWRS) which will assign a unique randomization number. Subjects will be randomized in a 2:2:1:1 ratio to receive APL-2 monthly (AM), APL-2 every-other-month (AEOM), sham injection monthly (SM) or sham injection every-other-month (SEOM), respectively. The randomization will be stratified by site.

The study is single-masked. Subjects and assessors of efficacy assessments (imaging or visual acuity) are masked to treatment (APL-2 or sham injection). The investigators, site personnel not performing efficacy assessments, vendors, sponsor and CRO personnel will be unmasked to treatment assignment. Additionally the CRC, who will perform the independent review of efficacy evaluation images, will be masked to provide an objective assessment of these evaluations.

The independent SMC will be provided unmasked safety data for their safety assessment.

Masking will be maintained throughout the conduct of the study. In the event of a medical emergency where the knowledge of subject treatment by masked individuals (e.g. the subject or his/her physician) is required, an individual Investigator will have the ability to unmask the treatment assignment for a specific subject and share that information with the appropriate parties. The Investigator must endeavour to notify the Sponsor prior to unmasking a subject.

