### 6. GENERAL ASPECTS FOR STATISTICAL ANALYSIS

#### 6.1. GENERAL METHODS

All statistical tests will be 2-sided at the 0.1 level of significance. To understand the clinical significance of the estimated treatment effects and to aid interpretation of the formal hypothesis testing 2-sided 95% CI will also be provided. There will not be any adjustments for multiple comparisons.

For all independent ophthalmic assessments (performed by DARC laboratory), if assessments by only two independent readers are available, then the mean of the 2 readings will be used in the calculation of summary statistics. If assessments by three independent readers are available, then the median of the three readings will be used for the summary calculations.

Continuous variables will be summarized using the number of non-missing observations (n), mean, standard deviation (SD), median, minimum, and maximum. Geometric mean and coefficient of variation (CV) will be included for PK parameters, where appropriate. Categorical variables will be summarized using frequencies and percentages. Unless stated otherwise, for all percentages, the number of subjects in the analysis population for the treatment group will be the denominator.

Unless otherwise specified, the estimated mean and median for a set of values should be printed out to 1 more decimal place than the original values, and standard deviations should be printed out to 2 more decimal places than the original values. The minimum and maximum should report the same number of decimal places as the original values. Percentages will be displayed with 1 decimal place; except percentages will not be presented when the count is zero and 100% will be presented as an integer.

Unless stated otherwise, baseline will be taken as the last available non-missing assessment prior to first study drug administration.

Subjects can discontinue treatment but remain in the study for follow-up. All assessments will be included in summary tables or analyses unless stated otherwise.

For all summary tables, data will be presented by treatment group and by pooled sham and pooled APL-2. For summaries by-visit pooled sham and pooled APL-2 will only be presented for the bi-monthly visits. The treatment group labels for summary tables will be:

- APL-2 Monthly
- APL-2 EOM
- APL-2 Pooled
- Sham Monthly
- Sham EOM
- Sham Pooled

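### SAP 8.1 lets the scale of the primary endpoint change after residuals are seen, without naming the alternative or saying that square root stays primary

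*SAP*

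**What the plan says.** **Scale.** Protocol 5.3: "The primary endpoint is the change in square root GA lesion size from baseline to Month 12 as measured by FAF". SAP 4.1 and 8.1 keep this scale. The sample size rests on it too. Protocol 11.3.1 assumes that, untreated, "average square root area lesion growth is 0.33mm/year", and Protocol 11.3.3 adds: "This study is designed to detect a 30% reduction in annual square root area increase".

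**Model and check.** SAP 8.1 fits an MMRM to Months 2, 6 and 12: "An unstructured covariance structure will be used to model the within subject error". The residuals then go through a Shapiro-Wilk test, and a p-value above 0.1 "will be considered proof of normality". At 0.1 or below, the residual plots are looked at for symmetry. Then: "If the evaluation of residuals indicates a problem with the model assumptions, another transformation of the data will be considered".

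**Who knows the arms.** SAP 3.4: "vendors, sponsor and CRO personnel will be unmasked to treatment assignment". Protocol 7.2 agrees.

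**Error rate.** SAP 6.1: "All statistical tests will be 2-sided at the 0.1 level of significance". The same section rules out multiplicity adjustment.

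**Status of the clause.** SAP 2 gives the SAP precedence over the protocol on analysis and sends departures from the SAP to the study report. Protocol 11.2.3.2 has no residual rule, and SAP 13 does not list this one among the changes from the protocol.

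**The concern.** The clause leaves five things open: which transformation, what counts as asymmetric, which residuals are tested (raw or scaled, pooled over visits or not), who decides, and whether the square-root result remains primary. The decision comes after outcome data are seen, and no masked residual review is planned. Because the SAP itself permits the change, making it need not count as a departure to be reported.

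A change of scale also changes the question. If square-root area grows by g from baseline s, area grows by 2sg + g². With g = 0.33 mm, at the two ends of the eligible range (2.5 and 17.5 mm², inclusion criterion 4a):

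- s = √2.5 = 1.58: 2 × 1.58 × 0.33 + 0.11 = 1.15 mm²
- s = √17.5 = 4.18: 2 × 4.18 × 0.33 + 0.11 = 2.87 mm²

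The same square-root growth is about 2.5 times larger in area for the largest lesions, so an area analysis weights eyes differently. Protocol 11.2.3.2 relies on square-root change being independent of baseline size.

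The trigger is also weak. A non-significant normality test proves nothing about normality, and a significant one can arise when the model is right.

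**Working it through.** **1. The plan's own figure.** Inputs: means 0.23 or 0.28 against 0.33 mm and 67 per group (Protocol 11.3.3), SD 0.20 (SAP 3.3 and 13), two-sided 10% level. For a three-group ANOVA, λ = n Σ(μᵢ − μ̄)² / σ² with 2 and 198 degrees of freedom.

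- 0.23, 0.23, 0.33 (and 0.23, 0.33, 0.33): Σ = 0.00667, λ = 67 × 0.00667 / 0.04 = 11.2, power 91.4%
- 0.23, 0.28, 0.33: Σ = 0.0050, λ = 8.4, power 82.6%

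These match the stated 91%, 91% and 83%. The power statement is tied to the square-root scale.

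**2. How often a correct model fails Shapiro-Wilk at 0.1.** Normal repeated measures were simulated for three groups of 67 at three visits, with 2,000 runs for each setting (rows marked * come from separate runs of the same kind). The Month 12 SD is 0.20. The Month 2 and Month 6 SDs are assumptions, because the documents give none. Ranges cover two assumed correlation patterns (0.5 to 0.7, and 0.3).

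| SD at Months 2 / 6 / 12 | Raw residuals, pooled | Scaled by fitted covariance | Raw test fails and \|skewness\| > 0.5 |
|---|---|---|---|
| 0.20 / 0.20 / 0.20 | 10–17% | about 10% | 0% |
| 0.14 / 0.17 / 0.20 | 23–31% | 9–12% | 0% |
| 0.12 / 0.15 / 0.20 * | about 55% | – | under 1% |
| 0.10 / 0.15 / 0.20 | 84% | 8–10% | under 0.2% |
| 0.082 / 0.141 / 0.20 | 98–99% | 9–10% | under 0.2% |
| 0.08 / 0.13 / 0.20 * | about 99% | – | under 1% |
| 0.033 / 0.10 / 0.20 | 100% | 9–10% | 1.5–2.2% |

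Month 12 residuals alone fail in about 10% of runs. The 0.5 skewness cut-off is an assumed stand-in for the plot review.

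The cause can be shown directly. Pooling normal residuals with variances vₖ gives skewness 0 and excess kurtosis 3·mean(v²)/mean(v)² − 3. For 0.10 / 0.15 / 0.20, mean(v) = 0.02417 and mean(v²) = 0.000735, so the excess is 3 × 1.259 − 3 = 0.78 (simulated 0.74 to 0.76). The pooled residuals are heavy-tailed but symmetric.

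**3. Cost of a free choice of scale.** 20,000 null trials were simulated with 67 per group, baseline area uniform over 2.5 to 17.5 mm², and square-root growth normal with mean 0.33 and SD 0.20 in every group. A Month 12 ANCOVA stands in for the MMRM. The simulation standard error is √(0.1 × 0.9 / 20,000) = 0.2 points.

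| Rule | Error of overall test |
|---|---|
| Square root fixed | 10.1% |
| Smaller p of square root and area | 12.0% |
| Smallest p of square root, area and log | 14.0% |

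**4. Cost when the two-step check is applied first.** 8,000 null trials per case were simulated for AM against sham. The switch was open only if Shapiro-Wilk p ≤ 0.1 and |skewness| > 0.5.

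- Normal growth: the switch opens in 0.6% of trials. Error is 10.2% even if the smallest of three p-values is then taken.
- Gamma growth, skewness 2 × 0.20 / 0.33 = 1.2: the switch opens in 99.8%. Error is 9.8% if the scale is chosen by residual symmetry and 13.5% if chosen by smallest p-value.

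**The case against.** Checking residuals and considering a transformation is ordinary practice, especially in Phase II, and the clause has two steps. A reader might infer that a failed Shapiro-Wilk test switches the endpoint and that, with unstructured covariance, failure is almost certain. The documents do not support that. The symmetry review stands between test and transformation, and residuals from a correct model are symmetric. High failure rates need raw residuals pooled over visits with rising SDs, and the SAP states neither the residual type nor those SDs. This part of the objection stands.

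The error figures of 12% and 14% also require someone to pick the smallest p-value, which the SAP does not prescribe, and log appears nowhere in the documents. SAP 8.1 further presents pairwise LSD p-values only after a significant treatment effect. With that condition the AM-against-sham error in the gamma case was 5.4% (square root) and 7.5% (best of three), both below 10%. This stands for the pairwise comparison, but the overall test carries the 12% to 14%.

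Finally, SAP 8.1.2 already analyses untransformed area, and SAP 8.1 and 8.1.1 require square-root summaries and a square-root LOCF analysis, so a square-root result could not vanish. That limits concealment, but it does not settle which result is primary. The symmetry review has no criterion, and a problem with model assumptions is wider than asymmetry, so the safeguard is unmasked judgement.

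**Conclusion.** The point holds at modest size. The primary scale is not fixed before the data are seen, and discretion over it lies with people who may know the arms. The normality test is a poor trigger: it fails a correct normal model about 10% of the time with scaled residuals, and about 55% to 99% for some assumed rising visit SDs if raw residuals are pooled. Those are rates of reaching the plot review, not of changing the endpoint.

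Among the scales examined, the overall 10% error rises to at most about 12% (square root or area) or 14% (with log). It stays near 10% if the scale is chosen by residual symmetry. These figures rest on the assumed SDs, correlations, growth distributions and skewness cut-off, and on a Month 12 ANCOVA in place of the MMRM.

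A reader might also infer that the option was used. Nothing in the documents suggests it. SAP V3.0 was revised after the 12-month results were reviewed (SAP 4.1 and 8.1.3), still names square root as primary, and lists no change of transformation. The clause remains live, because SAP 8 repeats the analyses at Month 18, and BCVA, foveal encroachment and SD-OCT lesion size are analysed in the same way.

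**What to change.** In SAP 8.1:

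- State that the MMRM on square-root area is the primary analysis whatever the residual check shows.
- Remove the Shapiro-Wilk rule as a trigger, with its claim of proof.
- Inspect residuals descriptively, scaled by the fitted covariance or visit by visit.

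In SAP 8.1.1, name any other scale, or a robust or rank analysis of Month 12 change, as a sensitivity analysis reported beside the unchanged primary result. State in the report that the square-root scale was used, if it was, and apply the same wording to the Month 18 repeat.

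The cost is SAP wording and one optional analysis run. Sample size and data collection are unaffected.
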